because of other reasons, their missing SRI at week 52 will be estimated using the multiple imputation method. The imputation values will be drawn from the categories formed by treatment group and randomization stratum to which the patient belongs. In the 2nd method, the missing SRI at week 52 will be imputed using the last observation carried forward (LOCF) method. In the 3rd method, patients who withdraw and those completers who used prohibited medication within 8 weeks from week 52 will be classified as nonresponders. Secondary efficacy variables will be summarized using the descriptive statistics by treatment group and time point. Safety evaluations will include all patients who took at least 1 dose of study drug. Descriptive statistics will be used to summary the safety variables.

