In order to ensure patient safety, patients who are determined to be treatment failures will be withdrawn from the study. Patients may be treated for treatment failure at the discretion of the investigator. Treatment failure is defined as any of the following:

- occurrence of a severe flare according to the SFI (also results in withdrawal from the study)
- increase in use of background oral corticosteroids beyond 80 mg of prednisone equivalent/week. (NOTE: Treatment of mild/moderate flare is permitted as detailed in section 5.2. The use of steroids for the treatment of a mild or moderate flare or for the treatment of conditions other than SLE will not be permitted beginning at week 44 [visit 14] through week 52 [visit 16].)
- initiation of pulse iv steroid therapy (ie, 250 to 1000 mg iv total daily dose of methylprednisolone)
- increase in the dose of immunosuppressive agents (methotrexate, azathioprine, MMF, leflunomide) above the baseline level
- initiation of new immunosuppressive therapy (cyclophosphamide, methotrexate, azathioprine, cyclosporin, tacrolimus, leflunomide, MMF)

- initiation of therapy with biologics for the treatment of SLEte, azathioprine, cyclosporin, tacrolimus, leflunomide, MMF)

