### **7.1 Adverse Events**

#### **7.1.1 Definition of an Adverse Event**

An adverse event is any untoward medical occurrence in a patient that develops or worsens in severity during the conduct of a clinical study of a pharmaceutical product and does not necessarily have a causal relationship to the study drug. An adverse event can, therefore, be any unfavorable and unintended physical sign, symptom, or laboratory parameter that develops or worsens in severity during the course of the study, or significant worsening of the disease under study (or any concurrent disease), whether or not considered related to the study drug.

Accordingly, an adverse event could include any of the following:

- intercurrent illnesses
- physical injuries
- events possibly related to concomitant medication
- significant worsening (change in nature, severity, or frequency) of the disease under study or other pre-existing conditions. (NOTE: A condition, recorded as pre-existing, that is intermittently symptomatic [eg, headache] and which occurs during the study should be

recorded as an adverse event.)

- drug interactions
- events occurring during diagnostic procedures or any washout phase of the study
- laboratory or diagnostic test abnormalities occurring after the start of the study (ie, after screening and once confirmed by repeat testing) that results in the withdrawal of the patient from the study, requires medical treatment or further diagnostic work-up, or is considered by the study investigator to be clinically significant.

NOTE: Abnormal laboratory test results at the screening visit that preclude a patient from entering the study or receiving study treatment are not considered adverse events, but will be recorded to monitor data from patients who do not meet screening criteria.

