#### **7.1.6 Withdrawal Due to an Adverse Event**

Any patient who experiences an adverse event may be withdrawn from the study at any time at the discretion of the investigator. If a patient is withdrawn wholly or in part because of an adverse event, both the adverse events page and termination page of the CRF will be completed at that time. In addition, a blood sample will be obtained for measurement of the concentration of IPP-201101 from all patients who have an adverse event assessed as related to study drug leading to withdrawal from the study (see also section 7.1.5.2). The patient will be monitored until the event has resolved or stabilized, until a determination of a cause unrelated to the study drug or study procedure is made, or until the patient is referred to the care of a local health care professional. The investigator must inform the medical monitor as soon as possible of all patients who are being considered for withdrawal due to adverse events. Additional reports must be provided when requested.

If a patient is withdrawn from the study for multiple reasons that include adverse events, the termination page of the CRF should indicate that the withdrawal was related to an adverse event.

Stopping rules and discontinuation criteria for any toxicity are described in section 3.6.

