#### **7.1.7 Withdrawal From the Study Due to Severe Flares**

A patient will be withdrawn from the study for a severe lupus flare as per the SFI as described in section 3.6.

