### **10.6.3 Planned Method of Analysis**

#### **10.6.3.1 Primary Efficacy Analysis**

The efficacy evaluation will be based on the full analysis set, which will include all patients who receive at least 1 dose of study drug. The statistical method to be used for the SRI is the logistic regression model with treatment and stratification factors as main factors. Patients who withdraw from the study are classified as nonresponders as measured by SRI at week 52 in the primary analysis. The SRI is linked to the model factors through the logit function. The

likelihood-ratio–based Chi-square statistics will be used for testing the treatment difference between IPP-201101 and placebo in SRI at week 52 at the significance level 0.05. The odds ratio (active/placebo) and associated 95% confidence interval will be determined from the logistic regression model.

As sensitivity analyses, the primary analysis will be repeated using another 3 imputation methods to estimate missing SRI at week 52 according to the reason for withdrawal. In the 1st method, patients who withdraw because of lack of efficacy will be classified as treatment failures assessed by SRI at week 52. For patients who withdraw because of other reasons, their missing SRI at week 52 will be estimated using the multiple imputation method (Little and Rubin, 2002). The imputation values will be drawn from the categories formed by treatment group and randomization stratum to which the patient belongs. In the 2nd method, the missing SRI at week 52 will be imputed using the last observation carried forward (LOCF) method. In the 3rd method, patients who withdraw and those completers who used prohibited medication within 8 weeks from week 52 will be classified as nonresponders.

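### Sensitivity method 1 imputes week-52 SRI from treatment-by-stratum cells that ignore the patient's own post-baseline assessments, and it identifies failures only by withdrawal reason (minor)

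*Protocol*

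**What the plan says.** Section 10.6.3.1 counts every withdrawal as a nonresponder in the primary analysis and then repeats the analysis under three other rules.

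- **Method 1.** Withdrawals because of lack of efficacy are failures. The rest are imputed: "For patients who withdraw because of other reasons, their missing SRI at week 52 will be estimated using the multiple imputation method". The source of the draws is fixed: "The imputation values will be drawn from the categories formed by treatment group and randomization stratum to which the patient belongs". The synopsis (Statistical Considerations) repeats the rule.
- **Method 2.** Here "the missing SRI at week 52 will be imputed using the last observation carried forward (LOCF) method".
- **Method 3.** All withdrawals, and completers with recent prohibited medication, are nonresponders.

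The strata (section 3.3) are region, screening SLEDAI-2K total score in two classes, and racial-ethnic group in two classes.

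On withdrawal itself, section 3.6 says that "patients who are determined to be treatment failures will be withdrawn from the study" and lists severe flare first among the criteria. Section 7.1.7 adds: "A patient will be withdrawn from the study for a severe lupus flare as per the SFI". Section 7.1.1 includes among possible adverse events "significant worsening (change in nature, severity, or frequency) of the disease under study". Section 7.1.6 gives the adverse event priority when several reasons apply; its coding rule reads in part "withdrawn from the study for multiple reasons that include adverse events, the termination page of the CRF should indicate that the withdrawal was related", the relation meant being the one with the adverse event.

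**The concern.** Method 1 is the only planned analysis that separates withdrawals by reason and the only one that uses multiple imputation. Its value lies in showing whether the primary result depends on scoring every withdrawal as a nonresponder. That needs a plausible prediction of what the withdrawn patients would have shown at week 52.

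The rule as written conditions on arm and pre-treatment factors only. A patient who had met the SRI at several consecutive visits before moving away, and one whose scores had risen steadily, are exchangeable if they share a cell.

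Selection by withdrawal reason is a second weakness. Nothing in the protocol ties the section 3.6 treatment-failure criteria to the lack-of-efficacy category that method 1 uses. A protocol-defined failure filed under another reason would be given a chance of response. Agreement between method 1 and the primary analysis would then be less reassuring than it appears.

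**Working it through.** **1. What enters the imputation.** Treatment group, region, screening SLEDAI-2K class and racial-ethnic class. None is measured after treatment starts.

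**2. What is collected and not used.** Table 2 schedules SLEDAI-2K, BILAG-2004, PhGA and SFI at weeks 4, 8, 12, and so on to 48, which is 12 on-treatment visits. Section 3.11.4 lists the same instruments at early termination, and section 4.3 asks for a complete final evaluation at withdrawal. All SRI components are therefore available up to the point of withdrawal.

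**3. Cell size.** Number of cells = 2 arms × 2 SLEDAI-2K classes × 2 racial-ethnic classes × R regions = 8R. R is not stated, but stratifying by region needs R ≥ 2.

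- R = 2: 16 cells, 200/16 = 12.5 patients on average.
- R = 5 (assumed): 40 cells, 200/40 = 5 on average.

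These averages are before withdrawals are removed. At an assumed 20% withdrawal they fall to 10 and 4 completers.

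**4. The route for a severe flare.** (a) It is a treatment failure with mandatory withdrawal (sections 3.6 and 7.1.7). (b) Worsening lupus may be recorded as an adverse event (7.1.1). (c) If an adverse event is among several withdrawal reasons, the termination page should show that (7.1.6). (d) Section 3.6 gives lack of efficacy and adverse event as separate examples of reasons for discontinuing. (e) Method 1 imputes whatever is not lack of efficacy. Each step is permitted by the text. None is shown to be the usual practice.

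**5. Labelled illustration only.** The protocol has no figure for method 1 and gives no withdrawal or flare rates. Its planning rates (section 10.2) are placebo 40% to 45% with a 25-point difference, so active 65% to 70%. The accompanying power claim reproduces with 100 per arm and an uncorrected chi-square test: 94.9% to 95.3% for 25 points (stated as 90% or more) and 81.2% to 81.6% for 20 points (stated as 80%).

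Those rates belong to an analysis in which withdrawals are already nonresponders. If w is the withdrawal proportion and only completers act as donors, the cell response rate is c = planning rate/(1 − w). With w = 20% assumed in both arms:

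- placebo: 0.40/0.8 = 0.500, 0.45/0.8 = 0.5625
- active: 0.65/0.8 = 0.8125, 0.70/0.8 = 0.875

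Let m0 and m1 be the section 3.6 failures per 100 patients on placebo and active that are imputed instead of scored as nonresponders. All other withdrawals are held as nonresponders to isolate the effect. The shift in the treatment difference, in percentage points, is m1·c1 − m0·c0.

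| Assumed m0, m1 | Shift (points) |
|---|---|
| 5, 5 | 4.06 − 2.50 = +1.56; 4.375 − 2.8125 = +1.56 |
| 5, 0 | −2.5 to −2.8 |
| 0, 5 | +4.1 to +4.4 |

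The net shift is zero when m0/m1 = c1/c0, that is 0.8125/0.500 = 1.63 or 0.875/0.5625 = 1.56. The sign therefore depends on counts that the protocol does not give. If patients already classed as lack-of-efficacy failures also serve as donors, which section 10.6.3.1 neither says nor excludes, c is lower and the shifts are smaller.

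**The case against.** The strongest reply is that section 10.6.3.1 offers a set of analyses and should be judged as a set. A severe-flare withdrawal scores zero in the primary analysis and in method 3, and LOCF uses the patient's own last data. This stands: no primary inference is at risk, and the point concerns one of three sensitivity analyses.

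Second, the flare route is unproven. Severe flare has its own heading (7.1.7), separate from withdrawal due to an adverse event (7.1.6). Section 3.6 calls it a treatment failure, the same term that method 1 applies to lack-of-efficacy withdrawals. A site could well record it as lack of efficacy, the CRF reason list is not shown, and a statistical analysis plan could supply the mapping. This also stands. A reader might infer that severe flares will be credited with response as if the patients were stable. The documents do not support that: the route is possible only, and the draw would be at the cell's average rate, which includes nonresponders.

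Third, imputation within arm and stratum is a recognised missing-at-random assumption, so adding post-baseline data is a preference. This stands only in part. The assumption is legitimate, but it requires that a patient's course before withdrawal carries no further information about week 52, which is hard to defend for repeated measures of the same index. The protocol fixes the cells explicitly, so this is a stated choice and not a detail left open.

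Fourth, scoring section 3.6 failures as nonresponders moves method 1 closer to the primary analysis. That is true, but withdrawals for consent, relocation or unrelated adverse events would still be imputed, so a real contrast remains.

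**Conclusion.** The point holds as a minor one. It is certain from the text that method 1 conditions on arm and pre-treatment strata alone, leaves the collected SRI components unused, and selects failures by withdrawal reason. It is arithmetic that the cells average at most 12.5 patients, given at least two regions. It is possible, but not shown, that section 3.6 failures such as severe flares would be imputed through adverse-event coding.

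A reader might go further and infer a bias in favour of the active arm, or take the table above as an estimate. Neither is supported. The counts and the 20% withdrawal are assumptions, the completer-only donor pool is an assumption, and the direction changes with the balance between arms. No size should be claimed beyond the illustration.

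**What to change.** Amend section 10.6.3.1 and the matching synopsis text for method 1 in two respects.

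1. Replace the cell draws by an imputation model containing treatment, the stratification factors as main effects, baseline SLEDAI-2K, and SRI status or its components at earlier visits, including early termination. Main effects avoid the thin cells.
2. State that, in method 1, a withdrawal triggered by a section 3.6 treatment-failure criterion is scored as nonresponse whatever reason is recorded, together with recorded lack of efficacy. This is an analysis rule keyed to the withdrawal that occurred. It leaves the section 3.6 and 5.2 rules as they are and does not count permitted treatment as failure.

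The cost is a few sentences and some programming. No new data are needed. The drawback is that the result then depends on an imputation model, which should be specified before unblinding.

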**Statistical Considerations:** The primary efficacy variable is the proportion of patients achieving a combined clinical response using the SRI at week 52. With 100 evaluable patients per group (200 total), this study will have a 90% or greater power to detect a 25% or greater difference or a 20% difference with a 80% power in the proportion of SRI responders between the IPP-201101 group and the placebo group. This projection using the Pearson Chi-square test (2-sided, alpha=0.05) is based on an anticipated placebo effect at week 52 of 40% to 45%. This range covers the placebo effect reported in the literature and in a Phase 2b, multicenter, randomized, double-blind, placebo-controlled dose-ranging study of IPP-201101 (study IP-004). The response rate under active is based on the Phase IIb study performed with the mannitol formulation outside the US. This study showed an absolute 25% response of active over placebo increasing to 40% in the interim analysis. Using a 80% or a 90%power leads to a sample size of 100 evaluable patients per group. The efficacy evaluation will be based on the full analysis set that includes all patients who received at least 1 dose of the study drug.. The statistical method to be used for the SRI is the logistic regression model with treatment and stratification factors as main factors. The SRI is linked to the model factors through the logit function. The likelihood-ratio-based Chi-square statistics will be used for testing the treatment difference between IPP-201101 and placebo in SRI at week 52 at the significance level 0.05. The odds ratio (active/placebo) and associated 95% confidence interval will be determined from the logistic regression model. As sensitivity analyses, the primary analysis will be repeated using another 3 imputation methods to estimate missing SRI at week 52 according to the reason for withdrawal. In the 1st method, patients who withdraw because of lack of efficacy will be classified as treatment failures assessed by SRI at week 52. For patients who withdraw

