## **10 STATISTICS**

### **10.1 Study Design and Randomization**

This is a Phase 3 randomized, double-blind, parallel-group, placebo-controlled study. Treatment assignment will be stratified for the following 3 baseline characteristics (as described in section 3.3): by region, SLEDAI-2K screening total score (6 to 9 or  $\geq 10$ ), and racial-ethnic group classification (black/Hispanic or others). Within each stratum, eligible patients will be randomly

assigned with a 1:1 ratio to receive either 200 mcg of IPP-201101 or placebo sc every 4 weeks for 48 weeks. Study investigators, patients, and ImmuPharma study staff will be blinded to the treatment assignments during the study.

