## **10.2 Sample Size and Power Considerations**

This study is designed to estimate and assess the significance of the difference between a 200-mcg dose of IPP-201101 and placebo in the proportion of SRI responders at week 52. With 100 evaluable patients per group (200 in total), this study will have 90% or greater power to detect a 25% or greater difference in the proportion of SRI responders between the IPP-201101 group and the placebo group or to detect a 20% difference with an 80% power. This projection using the Pearson

Chi-square test (2-sided,  $\alpha=0.05$ ) is based on an anticipated placebo effect at week 52 of 40% to 45%. This range covers the placebo effect reported in the literature ([Navarra et al 2009](#), [van Vollenhoven et al 2010](#), [Wallace et al 2009](#)) and in a Phase 2b, multicenter, randomized, double-blind, placebo-controlled dose-ranging study of IPP-201101 (study IP-004). The difference between placebo and active which is used in the sample size calculation is 25% based on the results of the Phase IIb study (IP-004) with the same formulation (Zimmer et al. ACR 2012)

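### The LOCF sensitivity analysis has no treatment-failure rule, so it can count protocol-defined failures as week-52 responders; the multiple-imputation analysis has a related gap

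*Protocol*

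**What the plan says.** Section 10.6.3.1 makes every withdrawn patient a nonresponder in the primary analysis, tested "at the significance level 0.05". It then lists three sensitivity analyses, introduced as imputing the week-52 SRI by why the patient withdrew:

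- Method 1 sets withdrawals for lack of efficacy to failure and multiply imputes the others within treatment group and randomization stratum.
- Method 2: "the missing SRI at week 52 will be imputed using the last observation carried forward (LOCF) method". The Synopsis (Statistical Considerations) says the same. Neither place states an exception.
- Method 3 keeps all withdrawals as nonresponders and adds completers who used prohibited medication in the last 8 weeks.

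Section 3.6 states that "patients who are determined to be treatment failures will be withdrawn from the study". Its list of failures contains severe flare and several medication events: background steroid above the weekly limit, intravenous pulse steroid, a raised immunosuppressant dose, a new immunosuppressant, or a biologic for SLE.

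The SRI (sections 3.2.1, 6.1 and 10.6.1) is built from SLEDAI-2K, PhGA and BILAG only. Withdrawn patients have their final assessments at the last visit (sections 3.1 and 3.11.4).

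**The concern.** Together these rules allow a result that contradicts the protocol's own definition of failure. A patient who starts a new immunosuppressant or a biologic must be withdrawn as a failure. If the SLEDAI-2K, PhGA and BILAG criteria happen to be met at the last visit, method 2 carries that patient to week 52 as a responder. Section 3.6 allows failures to be treated and does not fix when that treatment starts relative to the last assessment, so the added drug may even have produced the response.

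Method 2 also lets an early status stand for week 52. Table 2 schedules the SRI components from week 4 onward, so a week-4 or week-8 response can be carried to the end. The protocol's own earlier data show that response depends on time: in study IP-004 (section 1.3.2.3), among patients with a baseline SLEDAI-2K clinical score of at least 6, placebo SRI response was 38.6% at week 12 and 56.5% at week 24.

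Method 1 is only partly protected. Its failure rule depends on the code lack of efficacy, which is not tied to the section 3.6 list. Section 7.1.6 has withdrawals with several reasons recorded as adverse event if an adverse event is among them, and section 7.1.1 lets significant worsening of SLE count as an adverse event. A section 3.6 failure recorded that way is multiply imputed and may be drawn as a responder.

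At stake is how the supportive analyses are read. If method 2 disagrees with the primary result, the reader cannot tell fragility from an artefact of the carrying rule.

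**Working it through.** **1. The plan's own figures.** Section 10.2 states "With 100 evaluable patients per group (200 in total), this study will have 90% or greater power to detect a 25% or greater difference" "or to detect a 20% difference with an 80% power", for a placebo rate of 40% to 45%, with a 2-sided Pearson chi-square test at 0.05 and 1:1 allocation.

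Power = Φ{[d − 1.96·√(2·p̄(1−p̄)/n)] / √[(p1(1−p1)+p2(1−p2))/n]}, with n=100 and p̄ the mean of the two rates.

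- 40% v 60%: (0.20 − 1.96×0.0707)/0.0693 = 0.886, power 81.2%. For 45% v 65%: 81.6%.
- 40% v 65%: (0.25 − 1.96×0.0706)/0.0684 = 1.632, power 94.9%. For 45% v 70%: 95.3%.

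Both statements reproduce. Neither depends on the sensitivity analyses.

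**2. How each analysis treats a medication-based failure who met the SRI at the last visit.**

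| Analysis | Week-52 status |
|---|---|
| Primary | Nonresponder |
| Method 1, coded lack of efficacy | Nonresponder |
| Method 1, coded adverse event or other | Multiply imputed; can be a responder |
| Method 2 | Responder |
| Method 3 | Nonresponder |

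**3. Illustration over all withdrawals.** The protocol gives no withdrawal rate, so these counts are assumptions: 100 per arm, 15 active and 25 placebo withdrawals, and 55 v 40 responders under the primary rule. The test is z = |p1−p2| / √(2·p̄(1−p̄)/100), unadjusted for strata. Fractions are expected counts, left unrounded.

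- Primary rule: 55 v 40, p̄=0.475, z = 0.15/0.0706 = 2.12, p=0.034.
- 30% of withdrawals carried as responders in both arms: 55+4.5 = 59.5 v 40+7.5 = 47.5, p̄=0.535, z = 0.12/0.0705 = 1.70, p=0.089.
- 50% active and 30% placebo: 55+7.5 = 62.5 v 47.5, p̄=0.55, z = 0.15/0.0704 = 2.13, p=0.033.

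In the last case the difference stays at 15 points and the p-value hardly moves.

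**4. Illustration over treatment failures only.** This isolates the failure rule. Assume a borderline primary result of 54 v 40 (p=0.047), with a share q of failures having met the SRI at the last visit. Responders under method 2 = primary count + failures × q.

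| Failures, active / placebo | q | Responders | Difference | p |
|---|---|---|---|---|
| 10 / 10 | 0.6 | 60 v 46 | 14 | 0.047 |
| 10 / 20 | 0.2 | 56 v 44 | 12 | 0.090 |
| 10 / 20 | 0.6 | 60 v 52 | 8 | 0.25 |
| 20 / 10 | 0.2 | 58 v 42 | 16 | 0.024 |
| 20 / 10 | 0.6 | 66 v 46 | 20 | 0.004 |

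From a clearer primary result of 60 v 40 (p=0.005), the same q=0.6 gives 66 v 52 (p=0.044) with 10/20 failures and 72 v 46 (p=0.0002) with 20/10. At a common q, the direction depends on which arm has more failures.

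**The case against.** The case for leaving the plan alone has four parts.

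First, nothing confirmatory is touched: failures are withdrawn and withdrawals are nonresponders in the primary analysis. That stands.

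Second, the exposed group may be small. The carried value comes from the withdrawal visit; severe-flare patients will often fail the SRI there; and BILAG grade B itself denotes a need for more treatment (section 6.1). That stands in part. One new B is still compatible with response, and the medication-based failures remain exposed.

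Third, a reader might infer that the sensitivity analyses do not test the missing-data assumption at all. The documents do not support that. Method 1 replaces the nonresponder rule with multiple imputation by arm and stratum, and method 2 replaces it with frozen status. What is absent is a graded check by arm. A statistical analysis plan could add one, but the protocol already fixes LOCF without a failure rule, so that defect is not a matter of omitted detail.

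Fourth, LOCF is not alone in departing from the lead-in, because method 3 also makes no use of the withdrawal reason. That is correct. The mismatch with the lead-in is loose wording and weak evidence; the missing failure rule is the substance.

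**Conclusion.** The point holds as a defect in the supportive analyses. Followed as written, method 2 can count patients whom section 3.6 calls treatment failures as week-52 responders, and method 1 can do so when the coded reason is not lack of efficacy. The primary analysis, its 0.05 level, the sample size and the stated power are unaffected.

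The size is unknown because the protocol gives neither a withdrawal rate nor the share of failures who would meet the SRI at their last visit. Under the assumed figures, a p-value of 0.034 becomes 0.089 or stays at 0.033. In the failures-only illustration, 0.047 becomes anything from 0.004 to 0.25. These figures show sensitivity and are not forecasts.

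A reader might also infer that LOCF favours the active arm. The documents do not support a direction: with a common carried-response share, more failures on placebo shrinks the difference, more on active enlarges it, and equal numbers leave it unchanged. The change is worth making before unblinding, but the trial's main conclusion does not depend on it.

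**What to change.** In section 10.6.3.1 and the Synopsis, state that in methods 1 and 2 any patient meeting the section 3.6 treatment-failure definition is a nonresponder at week 52, whatever withdrawal reason is coded. Identify these patients from the recorded medication and flare data as well as from the termination page.

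Replace or supplement LOCF with a tipping-point analysis. Keep treatment failures and lack-of-efficacy withdrawals as nonresponders, vary the response probability of the remaining missing outcomes from 0 to 1 separately by arm, and report where the treatment test crosses 0.05. Reword the lead-in so that it no longer implies that every method uses the withdrawal reason.

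The cost is protocol and analysis-plan wording and a little more programming, with no new patients or visits. If LOCF is dropped altogether, comparability with older LOCF-based reports is reduced; keeping it beside the tipping-point analysis, with the failure rule added, avoids most of that loss.
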